Appendix F. Injection Instructions – Sample Pre-Filled Syringe

Subject Instructions

0.8 mL dose

(Administered as a single dose-pre-filled syringe)

Protocol M14-193

Tables of Contents

- Dosing Schedule
- General Information
- Injection Procedures

Study Drug Dosing Schedule

Subject Number: _____

You will require subcutaneous injections throughout the study.

You will receive the following number of injections during this study:

- Baseline visit (the first visit to receive study medication for this study), you will receive 2 injections at the investigation site subcutaneously.
- On or after Week 2 until Week 50, you will receive 1 injection (1 syringe from 1 package) subcutaneously.
- If the Investigator considers dose escalation is appropriate on or after Week 8, you will receive 2 injections (1 package).
- If you prefer to self-injection at home (or any place outside the investigation site), you will be allowed to do it after the site staff qualifies your skill of the administration procedures.

For all doses, packages of study medication must be used in the order dispensed.

Please return all used and unused syringes and empty boxes to the clinic on your next visit. Used syringes should be placed in the special sharps container provided. All unused syringes should be returned in the original box.

If an injection is missed or something occurs where the full dose cannot be injected, contact your study center immediately for further instructions.

Remember to complete your dosing sheet after each injection and to call the doctor's office if you are having problems administering your study medication.

General Information

- Pre-filled syringes will be labeled "Adalimumab."
- Store all adalimumab pre-filled syringes in your refrigerator NOT in the freezer. Should the syringes accidentally become frozen, call your study doctor's office.
- Study medication should be taken at about the same time of day, on the same day of the week as directed by your study doctor.
- **USE A NEW SYRINGE EVERY INJECTION DAY.** There may be medication left in the syringe. **DO NOT RE-USE.**
- Save all study medications. ***Pre-filled syringes (used and unused) & empty boxes must be returned to the study center at each visit.*** Used syringes will be disposed of in a sharps container provided to you.
- Call your doctor IMMEDIATELY if you experience any itching, hives, shortness of breath, or any symptom that has you concerned. If you are unable to reach your doctor or if you experience life-threatening symptoms, **call _____, or proceed to your nearest emergency room.**

[figure not shown]
Injection Procedures

1. Setting up for an injection

- Find a clean flat surface.
- Do not use if the seals on the carton are broken or missing. Contact your study doctor's office if the seals are broken.
- Take one package with the prefilled syringe(s) of adalimumab from the refrigerator. Do not use a prefilled syringe that has been frozen or if it has been left in direct sunlight.
- Return any unused syringe(s) to the refrigerator.

You will need the following items for each dose:

- study medication in pre-filled syringe(s)
- alcohol prep(s)
- cotton ball or gauze pad(s)

[figure not shown]

If you do not have all of the items you need to give yourself an injection, call your study physician. Use only the items provided in the box your adalimumab comes in.

- Make sure the liquid in the prefilled syringe is clear and colorless. Do not use a prefilled syringe if the liquid is cloudy or discolored or has flakes or particles in it.
- Have a special sharps (puncture proof) container nearby for disposing of used needles and syringes.

For your protection, it is important that you follow these instructions.

2. Choosing and preparing an injection site

[figure not shown]
- Wash your hands well.
- Choose a site on the front of your thighs or your stomach area (abdomen). If you choose your abdomen, you should avoid the area 2 inches around your belly button (navel).
- Choose a different site each time you give yourself an injection. Each new injection should be given at least one inch from a site you used before. Never inject into areas where the skin is tender, bruised, red or hard or where you have scars or stretch marks.
- If you have psoriasis, you should try not to inject directly into any raised, thick, red or scaly skin patches or lesions.
- You may find it helpful to keep notes on the location of your injection sites.
- Wipe the site where adalimumab is to be injected with an alcohol prep (swab), using a circular motion. Do not touch this area again until you are ready to inject.

3. How to prepare your adalimumab dose for injection with a Prefilled Syringe

- Hold the syringe upright with the needle facing down. Check to make sure that the amount of liquid in the syringe is the same or close to the 0.8 mL line for the 40 mg prefilled syringe. The top of the liquid may be curved. If the syringe does not have the correct amount of liquid, do not use that syringe. Call your study doctor.
- Remove the needle cover taking care not to touch the needle with your fingers or allow it to touch any surface.
- Turn the syringe so the needle is facing up and slowly push the plunger in to push the air in the syringe out through the needle. If a small drop of liquid comes out of the needle that is okay.
- Do not shake the syringe.

4. Injecting Adalimumab

- With your other hand, gently squeeze an area of the cleaned area of skin and hold it firmly.
- You will inject into this raised area of skin. Hold the syringe like a pencil at about a 45° angle (see picture) to the skin.
- With a quick, short, "dart-like" motion, push the needle into the skin.
- After the needle is in, let go of the skin. Pull back slightly on the plunger. If blood appears in the syringe it means that you have entered a blood vessel. Do not inject adalimumab. Pull the needle out of the skin and repeat the steps to choose and clean a new injection site. Do not use the same syringe. Dispose of it in your special sharps container. If no blood appears, slowly push the plunger all the way in until all of the adalimumab is injected.
- When the syringe is empty, remove the needle from the skin keeping it at the same angle it was when it was pushed into the skin.
- Press a cotton ball or gauze pad over the injection site and hold it for 10 seconds. Do not rub the injection site. You may have slight bleeding. This is normal.
- Dispose of the syringe right away into your special sharps container.

5. Training of "Dosing at home" for Japanese subjects

Training will include:

- a. Guidebook and DVD
 - How to transport and storage the study drug
 - How to perform self-injection
 - How to treat and collect the used syringe
 - How to do when the subject's physical condition is changed suddenly
 - How to fill in self-injection dosing sheet
- b. Practice of the SC injection under supervision by a physician or nurse

Following cases may expect to occur;

1. The same training course is necessary when a family member will perform subcutaneous injection.
2. If a subject gives up "dosing at home" or investigator decides a subject can no longer perform the self-injection appropriately, study drug should be administered by an investigator or nurse.
3. If the subject wants to terminate "dosing at home" or continuation of "dosing at home" becomes difficult, investigator should record the circumstances on the medical record and the study should continue with treatment by an investigator or nurse. In this case, record of Subject Dosing Sheet is not necessary afterward.

4. Even after the subject initiated "dosing at home," it is acceptable that an investigator or nurse performs the SC injection at the site, depending on the situation (e.g., time of dose escalation, this is not a protocol deviation). The reason why an investigator or nurse performed the injection should be recorded in the subject's medical record.
5. If the self-injection was once terminated and the subject wants to re-start it, investigator should confirm the subject can perform the self-injection appropriately. If it occurs after a long period (ca. 3 months or longer), investigator must confirm again the subject or his/her family member can perform the SC injection appropriately.

Appendix G. Subject Dosing Sheet for Self-Injection – Sample

M14-193 Subject ID:

#	Date	Wk	Number of Syringes	Time of Administration	Was the Entire Volume Injected?	Person Who Administer	Place	Injection Site (1 st Syringe)	Comments (Injection Site of 2 nd Syringe etc.)
1	2015/xx/xx	0	2	:	Y/N	Patient / Family	Home / Hospital	R/L, Abdomen/Thigh	no problem
2		2		:	Y/N	Patient / Family	Home / Hospital	R/L, Abdomen/Thigh	
3		4		:	Y/N	Patient / Family	Home / Hospital	R/L, Abdomen/Thigh	
4		6		:	Y/N	Patient / Family	Home / Hospital	R/L, Abdomen/Thigh	
5		8		:	Y/N	Patient / Family	Home / Hospital	R/L, Abdomen/Thigh	
6		10		:	Y/N	Patient / Family	Home / Hospital	R/L, Abdomen/Thigh	
7		12		:	Y/N	Patient / Family	Home / Hospital	R/L, Abdomen/Thigh	
8		14		:	Y/N	Patient / Family	Home / Hospital	R/L, Abdomen/Thigh	
9		16		:	Y/N	Patient / Family	Home / Hospital	R/L, Abdomen/Thigh	
10		18		:	Y/N	Patient / Family	Home / Hospital	R/L, Abdomen/Thigh	
11		20		:	Y/N	Patient / Family	Home / Hospital	R/L, Abdomen/Thigh	
12		22		:	Y/N	Patient / Family	Home / Hospital	R/L, Abdomen/Thigh	
13				:					
14				:					
15				:					

Appendix H. Severity Assessment Criteria from the Medical Care Guideline for Pustular Psoriasis (Generalized)

Total GPP Score and JDA Severity Index of GPP

Total GPP score = skin score + systemic/laboratory test score

JDA severity index of GPP: Mild (0 – 6), Moderate (7 – 10), Severe (11 – 17)

(1) Evaluation of Skin Score (0 – 9)

	Severe	Moderate	Mild	None
Erythema area (overall)*1	3	2	1	0
Erythema area with pustules*2	3	2	1	0
Edema area*2	3	2	1	0

*1 % of body surface area (severe, $\geq 75\%$; moderate, $\geq 25\%$ and $< 75\%$; mild, $< 25\%$).

*2 % of body surface area (severe, $\geq 50\%$; moderate, $\geq 10\%$ and $< 50\%$; mild, $< 10\%$).

(2) Evaluation of Systemic/Laboratory Test Score (0 - 8)

Score	2	1	0
Pyrexia (°C)	≥ 38.5	$38.5 > \geq 37$	$37 >$
White blood cell count (/ μ L)	$\geq 15,000$	$15,000 > \geq 10,000$	$10,000 >$
CRP (mg/dL)	≥ 7.0	$7.0 > \geq 0.3$	$0.3 >$
Serum albumin (g/dL)	$3.0 >$	$3.8 > \geq 3.0$	≥ 3.8

Appendix I. Efficacy Assessment Criteria

(1) The clinical response categories were defined according to the total skin score at Baseline.

Skin score at Baseline	Reduction in skin score				Increase in Skin Score	
	= 0	$\geq \Delta 3$	$\Delta 2$	$\Delta 1$		
4 – 9	Remission	Improvement	Improvement	Minimal improvement	Unchanged	Worsened
3	Remission	Remission	Improvement	Improvement	Unchanged	Worsened

- Clinical Response rate (%) = (Remission and Improvement)/number of treated patients *100

(2) Dose escalation criteria

In case subjects do not achieve improvement or remission (i.e., Minimal improvement, unchanged or worsened) on or after Week 8.

Appendix J. Observation of Skin Lesions – Example

Assessor Requirements

- The assessor must be a dermatologist or experienced physician.
- The same assessor must determine all skin lesion assessment for any individual subject throughout the trial. A backup assessor is only allowed in case of emergency or special situation when the designated assessor is unable to perform the evaluation. The backup assessor must be a dermatologist or an experienced physician.

Assessment of Skin Lesion and Record

Skin lesion should be an erythema, erythema with pustule, or edema, which is typical for GPP.

The Area (size) of erythema, erythema with pustule, or edema of each part of body will be assessed and recorded. Skin score of each skin lesion and total skin score will be calculated automatically, according to the scoring criteria by severity scores of 0 – 3 where higher scores denote worse conditions.

The site should make every attempt to have the same investigator conduct these assessments throughout the study for each subject.

Assignments for the following body regions are as follows:

- Neck: include with the head
- Buttocks: include with the lower extremities
- Axillae: include with the trunk
- Genitals: include with the trunk
- The inguinal canal separates the trunk and legs anteriorly

Appendix K. Skin Lesion Evaluation Form (GPP) and Scoring Form for Systemic Symptoms – Example

		Area of Skin Lesion (Body Surface Area)		
		Erythema (E)	Erythema with Pustule (P)	Edema (D)
Head	(max. 10%)	  %	  %	  %
Upper extremity	(max. 20%)	  %	  %	  %
Body Trunk	(max. 30%)	  %	  %	  %
Lower extremity	(max. 40%)	  %	  %	  %
Total	(max. 100%)	  %	  %	  %
Scoring Criteria		3: $\geq 75\%$, 2: $75\% > \geq 25\%$, 1: $25\% >$	3: $\geq 50\%$, 2: $50\% > \geq 10\%$, 1: $10\% >$	3: $\geq 50\%$, 2: $50\% > \geq 10\%$, 1: $10\% >$
Skin score (0 – 3)				
Total Skin score (0 – 9)				

BSA below 1% should be round up to integer number.

Scoring Form for Systemic Symptoms (GPP) – Example

	Pyrexia (Body temp., °C)	WBC (/µL)	CRP (mg/dL)	Serum albumin (g/dL)
Measurement	  . 	     	  . 	 . 
Scoring Criteria	2: ≥ 38.5 1: $38.5 > \geq 37$ 0: $37 >$	2: $\geq 15,000$ 1: $15,000 > \geq 10,000$ 0: $10,000 >$	2: ≥ 7.0 1: $7.0 > \geq 0.3$ 0: $0.3 >$	2: < 3.0 1: $3.8 > \geq 3.0$ 0: ≥ 3.8
Systemic score (0 – 2)				
Total Systemic score (0 – 8)				

JDA severity index in GPP: (Total Skin score + Total Systemic score)

Appendix L. PGA Scale for Generalized Pustular Psoriasis

The Physician's Global Assessment of Generalized Pustular Psoriasis (PGA-GPP) is a 6-point scale used to measure the severity of skin disease at the time of the qualified investigator's evaluation of the subject. The degree of overall severity will be evaluated using the following categories: erythema, pustulation, and edema.

Scoring Instructions:

If a subject has signs of erythema, pustulation, or edema intermediate between two grades, then the subject's erythema, postulation, or edema grade should be assigned the higher of the two grades. For example, if a subject's erythema is considered to be worse than 'mild' but less than 'moderate,' the subject's erythema grade should be considered 'moderate.'

The subject's score is an arithmetic average (mean) of the grades for erythema, pustulation, and edema, rounded to the nearest whole integer. For example, if a subject's erythema is moderate (3), **pustulation** is mild (2), and edema is moderate (3), the average grade is 2.67, which is rounded to the nearest whole integer of 3, giving the subject a score of 'moderate.'

Grade	Erythema	Pustulation	Edema	Score
0	No evidence of erythema	No evidence of postulation	No evidence of edema	Cleared, except for residual discoloration
1	Faint erythema	Scattered isolated pustules	Minimal edema	Minimal
2	Light red coloration	A cluster of non-confluent pustules involving 1 skin location	Mild edema	Mild
3	Moderate red coloration	Clusters of non-confluent pustules involving more than 1 skin location	Moderate edema	Moderate
4	Bright-red coloration	A confluent 'lake of pus' in 1 skin location	Marked edema	Severe
5	Dusky to deep-red coloration	Confluent 'lakes of pus' in more than 1 skin location	Severe edema	Very severe

'Treatment Success' is defined by at least 2 grade improvement relative to baseline:

- Very severe → Moderate or better
- Severe → Mild or better
- Moderate → Minimal or better
- Mild → Cleared

Appendix M. Psoriasis Area and Severity Index (PASI)

Assessor Requirements

- The assessor must be a dermatologist or experienced physician.
- The same assessor must determine all PASIs for any individual subject throughout the trial. A backup assessor is only allowed in case of emergency or special situation when the designated assessor is unable to perform the evaluation. The backup assessor must be a dermatologist or an experienced physician and have attended the PASI training session of the investigator meeting or have been trained by a physician who attended the investigator meeting.

PASI Scoring

Four anatomic sites – head, upper extremities, trunk, and lower extremities – are assessed for erythema, induration (plaque thickness), and desquamation (scaling) as seen on the day of the examination. The severity of each sign is assessed using a 5-point scale:

- 0 = No symptoms
- 1 = Slight
- 2 = Moderate
- 3 = Marked
- 4 = Very marked

The below table outlines the characteristics seen with each category:

	Erythema^a	Desquamation	Induration
0 = none	No redness	No scaling	No elevation over normal skin
1 = slight	Faint redness	Fine scale partially covering lesions	Slight but definite elevation, typically edges indistinct or sloped
2 = moderate	Red coloration	Fine to coarse scale covering most of all of the lesions	Moderate elevation with rough or sloped edges
3 = marked	Very or bright red coloration	Coarse, non-tenacious scale predominates covering most or all of the lesions	Marked elevation typically with hard or sharp edges
4 = very marked	Extreme red coloration; dusky to deep red coloration	Coarse, thick, tenacious scale over most or all lesions; rough surface	Very marked elevation typically with hard sharp edges

a. Do not include residual hyperpigmentation or, hypopigmentation as erythema.

The area affected by psoriasis within a given anatomic site is estimated as a percentage of the total area of that anatomic site and assigned a numerical value according to the degree of psoriatic involvement as follows:

- 0 = no involvement
- 1 = < 10%
- 2 = 10% to < 30%
- 3 = 30% to < 50%
- 4 = 50% to < 70%
- 5 = 70% to < 90%
- 6 = 90% to 100%

Assignments for the following body regions are as follows:

- Neck: include with the head
- Buttocks: include with the lower extremities
- Axillae: include with the trunk
- Genitals: include with the trunk
- The inguinal canal separates the trunk and legs anteriorly

The PASI score for each body region is obtained by multiplying the sum of the severity scores by the area score, then multiplying the result by the constant weighted value assigned to that body region. Since the head, upper extremities, trunk, and lower extremities correspond to approximately 10%, 20%, 30%, and 40% of body surface area, respectively, the PASI score is calculated using the formula.

$$\text{PASI} = 0.1(E_h + I_h + D_h)A_h + 0.2(E_u + I_u + D_u)A_u + 0.3(E_t + I_t + D_t)A_t + 0.4(E_l + I_l + D_l)A_l$$

Where E, I, D, and A denote erythema, induration, desquamation, and area, respectively, and *h*, *u*, *t*, and *l* denote head, upper extremities, trunk, and lower extremities, respectively. PASI ranges from 0.0 to 72.0 with the highest score representing complete erythroderma of the severest degree.

References for PASI

Appendix N. Work Sheet for PASI score

Evaluation Date: 20 / mon. / day

Subject ID:

BSA

Site	BSA	BSA (%)	BSA per Site (%)	Area Score
Head	max.10%	_____ %	× 10 =	A _h _____
Upper extremity	max. 20%	_____ %	× 5 =	A _u _____
Trunk	max.30%	_____ %	× 3.3 =	A _t _____
Lower extremity	max. 40%	_____ %	× 2.5 =	A _l _____
Total	100%			

Area score: 0 (0), 1 (10% >), 2 (30% > ≥ 10%), 3 (50% > ≥ 30%), 4 (70% > ≥ 50%), 5 (90% > ≥ 70%), 6 (100% ≥ 90%)

PASI Extent **0** (no symptom), **1** (mild), **2** (moderate), **3** (severe), **4** (very severe)

Items	Head (H)	Upper		Lower	
		Extremity (U)	Trunk (T)	Extremity (L)	
1. Extent of Erythema (E)	E _h _____	E _u _____	E _t _____	E _l _____	
2. Extent of Induration (I)	I _h _____	I _u _____	I _t _____	I _l _____	
3. Extent of Desquamation (D)	D _h _____	D _u _____	D _t _____	D _l _____	
4. Sum (1 + 2 + 3)					
5. Area score (A)	A _h _____	A _u _____	A _t _____	A _____	
6. Score per site (4 × 5)					
7. Portion of BSA	× 0.10	× 0.20	× 0.30	× 0.40	
8. PASI score per site (6 × 7)					
9.					PASI score (sum of 8)

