All subjects will be tested for the presence of the Hepatitis B Virus (HBV) at Screening. A positive result for the hepatitis B surface antigen (HBs Ag) will be exclusionary. Samples that are negative for HBs Ag will be tested for surface antibodies (HBs Ab) and core antibodies (HBc Ab Total). Subjects with HBs Ag (-), HBs Ab (-), and HBc Ab Total (+) require PCR qualitative testing for HBV DNA. Any HBV DNA PCR result that meets or exceeds detection sensitivity will be exclusionary.

Subjects with a negative HBs Ag test and tests showing the results below do not require HBV DNA PCR qualitative testing, and can be eligible to the study;

- HBs Ab (-) and HBc Ab Total (-)
- HBs Ab (+) and HBc Ab Total (-)
- HBs Ab (+) and HBc Ab Total (+)

Hepatitis C Screen

All subjects will be tested for the presence of the Hepatitis C Virus (HCV) at Screening. A positive result for the hepatitis C will be exclusionary.

Antinuclear Antibody and Anti-Double-Stranded DNA

ANA will be performed and if positive, anti-dsDNA will be performed at Screening as indicated.

Photography

Photography of skin lesions will be recorded for subjects who agree to be taken in the pre-selected sites at the time points noted in [Table 1](#). Photography will be used for referring changes of skin lesions from the Baseline over time, for the selected skin lesions at the discretion of the investigator. When photography is conducted, it will be recorded in the medical record appropriately.

Skin Lesions Outcome Assessments

The assessor must be a dermatologist or experienced physician. The site will make every attempt to have the same investigator perform the assessment of skin lesions throughout the study for each subject.

GPP Skin Score and BSA (Body Surface Area)

Skin lesion will be observed and assessed BSA for each skin symptom (erythema, erythema with pustule, and edema [[Appendix J](#)]) and to calculate skin score ([Appendix H](#)) at the time points indicated in [Table 1](#). BSA of GPP is relevant to BSA of erythema in GPP.

BSA, a proportion of skin lesion area in the total body surface area will be determined. The following should be taken into account for the assessment that four anatomic sites – the head, upper extremities, trunk, and lower extremities correspond to approximately 10%, 20%, 30%, and 40% of body surface area, respectively, and the palm corresponds approximately 1% of BSA. BSA below 1% should be round up to integer number in the assessment.

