Systemic Symptom/Laboratory Test Score

Systemic symptom/Laboratory test score in JDA severity index of GPP will be calculated from the result of Vital signs (body temperature) and Laboratory test (WBC, hs -CRP and serum Albumin) at the time points indicated in [Table 1 \(Appendix K\)](#).

PGA (Physician's Global Assessment)

A Physician's Global Assessment (PGA) of disease severity will be performed by the investigator at the time points indicated in [Table 1](#). The PGA is static and refers to the subject's disease state at the time of the assessment and is not a comparison with the subject's previous disease state, whether at the Baseline or at the previous visits ([Appendix L](#)).

Psoriasis Area and Severity Index Score (PASI Score)

A qualified investigator will assess the PASI score ([Appendix M](#)) at the time points indicated in [Table 1](#). All raw data used to determine the PASI score will be recorded on a worksheet ([Appendix N](#)) and entered to eCRF. The PASI score will be calculated on the EDC system automatically.

DLQI (Dermatology Life Quality Index)

Subjects will complete a DLQI questionnaire ([Appendix O](#)) at the Baseline, Weeks 8, 16, 24, 36 or 52/PD visit. The subject will complete the questionnaire by oneself or with the aid of site personnel, if necessary, before the investigator performs any clinical assessment to avoid biasing the subject's response. Sites will review the subject's questionnaires/assessments to make sure that they are complete before the subject completes the study visit and clarify any discrepancies with the subject before the visit is over to ensure accuracy.

SF-36v2™ Health Status Survey

The SF-36v2™ form contains 36 total questions targeting a subject's functional health and well-being, as well as his/her psychometric physical and mental health. Subjects will

complete the SF-36 at the visits indicated in [Table 1 \(Appendix P\)](#). The subject will complete the questionnaire by oneself or with the aid of site personnel, if necessary, before the investigator performs any clinical assessment to avoid biasing the subject's response. Sites will review the subject's questionnaires/assessments to make sure that they are complete before the subject completes the study visit and clarify any discrepancies with the subject before the visit is over to ensure accuracy.

Study Drug Dispensing/Administration

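### The PASI worksheet converts trunk BSA with the rounded factor 3.3 instead of 100/30, so trunk values at a cut-off score one area step too low if the sheet is followed as printed (minor)

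*Protocol*

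**What the plan says.** Protocol Appendix M defines the PASI area component regionally: the affected area "is estimated as a percentage of the total area of that anatomic site". It is scored 1 to 6 with lower bounds of 10, 30, 50, 70 and 90%, each bound belonging to the higher score. Appendix M also gives the regional shares, which "correspond to approximately 10%, 20%, 30%, and 40% of body surface area, respectively", and weights the trunk by 0.3 in the PASI formula.

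The Appendix N worksheet works from BSA. It has one column for BSA (maxima 10, 20, 30 and 40% for head, upper extremity, trunk and lower extremity), one for the percentage of the site, and one for the area score. The printed multipliers from the first column to the second are 10, 5, 3.3 and 2.5. Its scoring line, which begins "Area score: 0 (0), 1 (10% >), 2 (30% > ≥ 10%), 3 (50% > ≥ 30", uses the Appendix M cut-offs.

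On data flow, Protocol Section 5.3.1.1 states: "All raw data used to determine the PASI score will be recorded on a worksheet". These data are entered to the eCRF, and "The PASI score will be calculated on the EDC system automatically". PASI 50, 75 and 90 and the change and percent change in PASI are secondary variables (Protocol Section 5.3.3.2; SAP Section 10.3). SAP Section 7.1 also categorises baseline PASI at 10 and 30.

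**The concern.** Three of the four multipliers equal 100 divided by the regional maximum. The trunk multiplier is that quotient cut to one decimal. A factor that is slightly too small does no harm between cut-offs, but all five cut-offs fall on whole-number trunk BSA values, and the bounds are inclusive. A patient whose trunk is exactly 10, 30, 50, 70 or 90% involved therefore lands just below the bound on the worksheet and at the bound under Appendix M. The two appendices then give different area scores for the same patient.

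The error always lowers the trunk score. At follow-up it makes improvement look larger; at Baseline it makes improvement look smaller. It can therefore add or remove a PASI responder. If all 10 planned subjects are in the denominator, one changed subject moves a response rate by 10 percentage points.

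**Working it through.** **Inputs.** Regional maxima 10, 20, 30, 40% and multipliers 10, 5, 3.3, 2.5 (Appendix N); cut-offs 10, 30, 50, 70, 90%, lower bound inclusive (Appendices M and N); trunk weight 0.3 (Appendix M).

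**Step 1: the factors.** Exact factor = 100 / regional maximum.
- Head: 100/10 = 10, as printed.
- Upper extremity: 100/20 = 5, as printed.
- Lower extremity: 100/40 = 2.5, as printed.
- Trunk: 100/30 = 3.333; printed 3.3.

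**Step 2: area scores.** Over every whole-number BSA value in all four regions, the printed and exact factors give different scores only at these trunk values:

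| Trunk BSA | Exact % of trunk | Score | BSA × 3.3 | Score | Score if product rounded to whole % |
|---|---|---|---|---|---|
| 3 | 10 | 2 | 9.9 | 1 | 2 |
| 9 | 30 | 3 | 29.7 | 2 | 3 |
| 15 | 50 | 4 | 49.5 | 3 | 4 |
| 21 | 70 | 5 | 69.3 | 4 | 4 |
| 27 | 90 | 6 | 89.1 | 5 | 5 |

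That is 5 of 30 non-zero whole numbers (17%). A fully involved trunk (30 × 3.3 = 99%) still scores 6, so the PASI maximum of 72.0 is preserved.

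**Step 3: continuous scale.** For a cut-off c, the affected band runs from 0.3c up to c/3.3: 3 to 3.03, 9 to 9.09, 15 to 15.15, 21 to 21.21 and 27 to 27.27. The widths sum to 0.03 + 0.09 + 0.15 + 0.21 + 0.27, about 0.76 points with unrounded ends; 0.76/30 is about 2.5%.

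**Step 4: effect on PASI.** One area step on the trunk changes PASI by 0.3 × (E+I+D). The sum is at most 12, so the maximum is 0.3 × 12 = 3.6 points.

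**Step 5: can a responder flip?** Take the same severity sum S and the same true area score A in all four regions. PASI is then S × A, and a trunk error subtracts 0.3 × S.

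- *PASI 75 gained.* Baseline S = 3, A = 5, trunk 22% BSA: 15.0 by either factor. Follow-up S = 2, A = 2, trunk 3% BSA: exact 4.0; worksheet 4.0 − 0.6 = 3.4. Reduction 11.0/15.0 = 73.3% against 11.6/15.0 = 77.3%.
- *PASI 75 lost.* Baseline S = 3, A = 4, trunk 15% BSA: exact 12.0; worksheet 12.0 − 0.9 = 11.1. Follow-up S = 1, A = 3, trunk 10% BSA: 3.0 by either factor. Reduction 9.0/12.0 = 75.0% against 8.1/11.1 = 73.0%.

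The same construction flips the other thresholds:
- PASI 50 gained: Baseline 15.0, follow-up 8.0 against 7.4; 46.7% against 50.7%.
- PASI 50 lost: Baseline 6.0 against 5.1, follow-up 3.0; 50.0% against 41.2%.
- PASI 90 gained: Baseline 18.0, follow-up 2.0 against 1.7; 88.9% against 90.6%.
- PASI 90 lost: Baseline 20.0 against 18.8, follow-up 2.0; 90.0% against 89.4%.

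**Step 6: does the error reach the reported score?**
- Raw trunk BSA entered, EDC uses 100/30: no effect.
- Raw trunk BSA entered, EDC uses 3.3: affected.
- Site-derived area score (or converted percentage) entered: affected.

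The documents do not say which applies.

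**The case against.** The strongest reply is that PASI is computed by the EDC system, not by hand. If raw trunk BSA is keyed in and the system follows Appendix M, no reported value changes. This stands. A reader might infer from the worksheet that the reported PASI 50, 75 and 90 rates are wrong; the documents support only that they may be, through an unstated entry route.

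Second, a site may write the product as a whole percent. Three of the five cut-offs then recover and only 21% and 27% stay low. The worksheet states no rounding rule in either direction, so both cases remain open.

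Third, the 17% figure presumes whole-number BSA with every value equally likely. Appendix N does not require whole numbers, and on a continuous scale the share is about 2.5%. Against this, visual estimates tend to be round, and 10%, 30% or 50% of a region is a natural reading, so 2.5% may be too low. The documents give no distribution of trunk involvement, so neither figure is a rate of mis-scored visits.

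Fourth, the regional shares are themselves approximate, and a 1% relative error in the factor is small beside the uncertainty of visual estimation. That is fair. The difference is that this error is systematic, has a known direction and can be removed.

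Fifth, the worked examples were chosen to sit on an area cut-off and near a response threshold. They show that a flip is possible, not that it is likely.

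A reader might also combine the worksheet with the rule "BSA below 1% should be round up to integer number in the assessment" and conclude that head area score 1 can never occur, because 1% BSA is 10% of the head. The documents do not support that: the rule is given for the GPP skin score in Section 5.3.1.1 and on the Appendix K form, and neither Appendix M nor Appendix N carries it over to PASI.

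**Conclusion.** The trunk constant is wrong as printed: it contradicts the regional definition in Appendix M, and Appendix N is exact for the other three regions. With an unrounded product, trunk BSA at any of the five cut-offs, or up to 0.03 to 0.27 points above, scores one area step low, which costs at most 3.6 PASI points. PASI response can change in either direction. A change needs both a trunk value in one of these narrow bands and a percent reduction close to a threshold, so flips should be uncommon.

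The effect on reported results is conditional on what is entered and which factor the EDC uses. Only PASI-based secondary variables and the baseline PASI category are exposed; SAP Section 10.1 treats the efficacy analysis as descriptive with no significance level. The inference that the primary result is at risk would be mistaken: Clinical Response is built on the JDA skin score from total BSA (Appendices H, I and K) and never uses this factor. Severity: minor.

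**What to change.** In the trunk row of Appendix N, replace × 3.3 with ÷ 30 × 100 (equivalently × 10/3). Confirm, and record with the PASI derivation, which worksheet field is entered to the eCRF and that the EDC derives the trunk area score with the exact factor. For data already collected, recompute the trunk area score and PASI from recorded trunk BSA where it is held; the worksheet has a column for it.

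The cost is one constant on a form, one check of the EDC specification and, if that check fails, a programmed recalculation. No new assessments are needed where trunk BSA was recorded.
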